The study protocol was pre-registered at ClinicalTrials.gov NCT04573972 <https://clinicaltrials.gov/ct2/show/NCT04573972> prior to any data collection. Clinical Trials pre-registrations do not include analysis plans. Consequently, this OSF pre-registration, including an analysis plan, was filed prior to downloading any data from W2H.

Participant flow diagram: ([name] or [name], please fill in numbers)

XXX people entered W2H portal	→ XX did not consent
↓ XX consented	→ XX did not fully enroll
↓ XX fully enrolled	→ XX not linked to a fully-enrolled partner
↓ XX has fully-enrolled partner	→ XX did not provide synced FitBit & Aware data for at least 1 out of 7 days of pre-intervention period or has partner who did not provide synced data for 1 out of 7 pre-intervention days
↓ XX provides baseline data	→ XX requested to be unenrolled prior to randomization
↓ XX included in study and randomized to condition (N= XX/2 pairs)	
↓ XX in the regular incentive condition & YY in the social incentive condition	

Data collection procedures

Study participants were recruited at Carnegie Mellon University through posting on the subject pool website and announcements to undergraduate classes. Potential participants had to sign up with a friend, with at least one member of the friend pair being a current CMU student. Participants had to own an IOS or Android smartphone and be willing to download the FITBit and Aware apps to track their activity and location for 5 weeks.

Stopping rule

Our stopping rule was to close enrollment once 220 people were fully enrolled or when Oct 15, 2020 occurs, whichever comes first. We opened enrollment on Oct 1, 2020 and closed it on Oct 11, 2020 because at that point 220 people had fully enrolled. Fully enrolling includes consenting, completing the intake survey, providing a code for a partner who was also enrolling, and downloading the FitBit and Aware apps. Some of the individuals who fully enrolled were not included in the study because their partner did not fully enroll.

Manipulated variables

There was one manipulated variable (treatment condition) with two levels: regular vs. social incentive.

Measured variables

Primary dependent variables (as pre-registered on Clinical Trials)

1. The mean daily treatment period step count (averaged across all of a participant's included treatment period days) minus the mean daily baseline period step count (averaged across all of a participant's included baseline period days).

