2. The mean daily followup period step count (averaged across all of a participant's included followup period days) minus the mean daily baseline period step count (averaged across all of a participant's included baseline period days).
3. Number of days during treatment period when participant reached goal. Converted to a fraction by dividing by the number of included treatment period days.
4. Number of days during followup period when participant reached goal. Converted to a fraction by dividing by the number of included followup period days.
5. Change in score on UCLA Loneliness Scale. Score on post-test (range 0 to 60) minus score on pretest.

Secondary dependent variables (as pre-registered on Clinical Trials)

6. Number of days participant walked together with partner during treatment period, as assessed via self-report on daily survey

7. Number of days participant walked together with partner during followup period, as assessed via self-report on daily survey
8. Number of days participant walked together with partner during treatment period, as assessed via Aware data
9. Number of days participant walked together with partner during followup period, as assessed via Aware data

Indices

The UCLA Loneliness Scale is measured on both the intake and exit surveys. It consists of 20 items, each scored as 0, 1, 2, or 3. The scores from all 20 items are added to form a total score ranging from 0 to 60.

Inclusion Criteria

In order to be included in the study, each participant must fulfill all of the following

- Consent
- Fully enroll, including authorizing FitBit app and installing Aware app
- Link to a friend who fully enrolls in the study before the registration deadline
- Participants who request to unenroll are excluded.
- Provide synced step data for at least one day of the 7-day baseline period
 - That is, there must be at least one baseline day with a non-zero step count
- Provide Aware data for at least one day of the 7-day baseline period

Exclusion of individual data points

- Days that a participant has a value of 0 for steps walked will be considered missing data (assume there was no sync for that day)
- For each participant, we will compute the mean and standard deviation of number of daily steps, computed over all days of the study with non-zero step counts. Days with a step count that are > 3 standard deviations away from the participant's own mean will be excluded from analyses (treated as missing data).

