- Average step count will then be computed for each phase, after treating these excluded data points as missing.

Data File Structure

- Note: remove the research team participants from the datafile.
- Daily file (35 rows per participant -- one row per day of the protocol)
 - Subject id
 - Dyad id (links together the two subject ids in a friend pair)

- Phase (baseline, incentive, followup)
- Day of protocol (1 - 35)
- Calendar date
- FitBit steps walked
- Met goal (yes or no; missing for baseline period)
- Synced FitBit data (yes or no)
- Synced Aware data (yes or no)
- Correct end-of-day survey sent (yes or no; missing for baseline period)
- Answered end-of-day survey (yes or no; missing for baseline period)
- Walked with partner (yes or no; missing if wrong survey sent or survey not answered)
- Walked at least 2,000 steps with partner (yes, no, or missing)
- Walked in-person or virtually with partner
- Study file (1 row per participant)
 - Subject id
 - Included in study (for ITT analysis)
 - Included in main analysis
 - Dyad id (links together the two subject ids in a friend pair)
 - Date started baseline period
 - Date started incentive period
 - Goal number of steps
 - Total amount earned during study
 - All responses from baseline survey
 - All responses from exit survey

ITT analysis

- Includes all Ss who meet the inclusion criteria, even if they have a lot of missing data.
- Similar to the main analysis described below, but it doesn't exclude Ss based on missing data.
- It does still exclude individual data points, same as in the Main Analysis

Main Analysis

In order to be included in the main analyses, each participant must also fulfill all of the following

- Provide synced step data for at least 2 days of the 7-day baseline period
- Provide synced step data for at least 4 days of the 14-day treatment period
- Provide synced step data for at least 4 days of the 14-day followup period
- Be paired with a partner who is also included in the main analyses

Secondary Analyses

- Secondary analyses will explore the relationships among change in UCLA Loneliness score (intake to exit survey), change in mean daily steps walked from baseline to post-incentive period, and percentage of days during post-incentive period when the dyad walked together. Specifically, we will test whether the effect of study condition on change in steps walked is mediated by change in loneliness score and percentage of days when the dyad walked together.

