- Two boot-strapped mediation analyses will be conducted, one for each putative mediator.

Primary dependent variables (as pre-registered on Clinical Trials)

1. The mean daily treatment period step count (averaged across all of a participant's included treatment period days) minus the mean daily baseline period step count (averaged across all of a participant's included baseline period days).
2. The mean daily followup period step count (averaged across all of a participant's included followup period days) minus the mean daily baseline period step count (averaged across all of a participant's included baseline period days).
3. Number of days during treatment period when participant reached goal. Converted to a fraction by dividing by the number of included treatment period days.
4. Number of days during followup period when participant reached goal. Converted to a fraction by dividing by the number of included followup period days.
5. Change in score on UCLA Loneliness Scale. Score on post-test (range 0 to 60) minus score on pretest.

Secondary dependent variables (as pre-registered on Clinical Trials)

6. Number of days participant walked together with partner during treatment period, as assessed via self-report on daily survey
7. Number of days participant walked together with partner during followup period, as assessed via self-report on daily survey
8. Number of days participant walked together with partner during treatment period, as assessed via Aware data
9. Number of days participant walked together with partner during followup period, as assessed via Aware data

Main Analysis

- DV = each of the primary dependent variables shown above
- IV = condition (regular vs. social incentive)
- Data structure: 1 rows of data per participant
- Errors clustered at the dyad level
- Covariates:
 - Partners in same or different time zone (dyad level)
 - Gender, age (individual level)
 - Date of first day of baseline (individual level)
 - Lag in number of days between enrollment of first partner and enrollment of second partner (dyad level)

Exploratory HLM Analysis

- DV = daily step count
- IV
 - Fixed effect of participant
 - Dummy variable for treatment period (relative to baseline period as reference)
 - Dummy variable for followup period (relative to baseline period as reference)
 - Interaction between each dummy & condition (regular vs. social incentive)
- Data structure: 35 rows of data per participant (one for each day)

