- Clustering: days nested within participant; participant nested within dyad

Transformations

None planned.

Inference criteria

Alpha is set at .05

Data exclusion

See analysis plan

Missing data

When a participant is missing step data for an individual day, the mean daily step count for the study phase will be computed using the days with non-missing data. If a participant is missing step data for all the days in a study phase, the mean daily step count for the baseline period will be substituted (leading to a change score of 0).

If a participant is missing data from the intake survey (e.g., gender, age, or UCLA loneliness score), the study-wide mean or mode will be substituted. If a participant is missing data from the exit survey (e.g, UCLA loneliness score), the corresponding value from the intake survey will be substituted.

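### A missing intake UCLA score is filled with the study-wide mean, so that person's primary DV 5, and the loneliness mediator, becomes exit score minus cohort average and not within-person change

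*SAP*

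**What the plan says.** The Missing data section, identical in Protocol and SAP, treats gender, age and the intake loneliness score alike: for a missing "UCLA loneliness score), the study-wide mean or mode will be substituted". A missing exit score is handled differently: "the corresponding value from the intake survey will be substituted".

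Primary DV 5 (SAP, Measured variables) is "Score on post-test (range 0 to 60) minus score on pretest". The Indices section describes the scale: "It consists of 20 items, each scored as 0, 1, 2, or 3", and "The scores from all 20 items are added to form a total score ranging from 0 to 60". It gives no prorating rule, no minimum number of items and no item-level rule.

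The individual-level covariates in the SAP's Main Analysis are "Gender, age (individual level") and the date of the first baseline day. Intake loneliness is not among them. Under Secondary Analyses, change in loneliness is one of two mediators of the effect on step change.

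Two other statements bear on how often the rule applies and whether it can be improved. Under Stopping rule, "Fully enrolling includes consenting, completing the intake survey, providing a code for a partner who was also enrolling". Under Data File Structure, the study file keeps "All responses from baseline survey" and the same from the exit survey.

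**The concern.** Filling a covariate such as age with a cohort mean does little harm. The intake loneliness score is different because it is half of a primary outcome. Once it is replaced by a constant, DV 5 is the exit score measured from the cohort average. A person who is steadily lonely is recorded as having become lonelier, and one who is steadily not lonely as having improved. The model has no intake loneliness term to offset this.

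The rule also departs from the plan's handling of other outcome gaps, which are filled from the same person's data: other days in the phase, the person's own baseline steps, or the person's own intake score. A person with no baseline steps is excluded and is not given a cohort mean.

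At stake are the precision of DV 5 and the size of the indirect effect through loneliness. If the rule is applied to the 20-item total, up to 19 valid answers could also be discarded.

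**Working it through.** **Inputs.** From the documents: the DV 5 definition, the 20-item sum (20 x 3 = 60, which matches the stated range), the two substitution rules, the covariate list, and randomization at the end of baseline. The plan gives no SD, correlation, missingness rate or power figure for DV 5, so there is no stated figure to reproduce. Assumed: SD 10 at both intake and exit, intake-exit correlation rho of 0.6 to 0.8, share filled f of 5% or 10%, and a cohort mean of 20 in the example. The mean is used as the filled value because the score is numeric.

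**1. One person, one skipped item, rule applied to the total.** The true intake lies between the 19-item sum and that sum plus 3.

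| 19-item sum | Exit | True change | Entered with cohort mean 20 | Prorated (sum x 20/19) |
|---|---|---|---|---|
| 38 | 40 | -1 to +2 | +20 | 0 |
| 20 | 21 | -2 to +1 | +1 | -0.05 |
| 5 | 6 | -2 to +1 | -14 | +0.74 |

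If the exit score is missing too, the filled intake value is carried forward and the change is 0.

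**2. Variance.** True change has variance 2 x SD² x (1 - rho), giving SDs of 8.9, 7.7 and 6.3 at rho 0.6, 0.7 and 0.8. The entered value has variance SD², so its SD is 10. The ratio is 1/(2(1 - rho)): 1.25, 1.67 and 2.5. It is 1.00 at rho 0.5 and 0.71 at rho 0.3. The overall variance factor is (1 - f) + f/(2(1 - rho)).

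**3. Information kept.** The correlation of the entered value with true change is sqrt((1 - rho)/2): 0.45, 0.39 and 0.32 at rho 0.6, 0.7 and 0.8.

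**4. Mediator slope.** Assume that intake relates to step change only through loneliness change. Among filled cases the slope is (1 - rho) of its true value. Over everyone, with c = 2(1 - rho), the factor is (1 - f/2)c / ((1 - f)c + f). For example, at f = 5% and rho 0.8 it is 0.975 x 0.4 / (0.95 x 0.4 + 0.05) = 0.39/0.43 = 0.907.

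**5. Dropping these people instead.** The variance of the estimate is multiplied by 1/(1 - f).

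| f | rho | Variance factor, plan's rule | Variance factor, dropped | Slope factor, plan's rule |
|---|---|---|---|---|
| 5% | 0.6 | 1.013 | 1.053 | 0.963 |
| 5% | 0.7 | 1.033 | 1.053 | 0.944 |
| 5% | 0.8 | 1.075 | 1.053 | 0.907 |
| 10% | 0.6 | 1.025 | 1.111 | 0.927 |
| 10% | 0.7 | 1.067 | 1.111 | 0.891 |
| 10% | 0.8 | 1.150 | 1.111 | 0.826 |

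The two variance factors are equal when 1/(2(1 - rho)) = (2 - f)/(1 - f). At f = 5% this is 1.95/0.95 = 2.053, so rho = 0.756; at f = 10% it is 1.9/0.9 = 2.111, so rho = 0.763.

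**6. Arm contrast.** In a simulation with 110 independent people per arm, rho 0.7 and no true effect, 5% missing in each arm gave mean arm differences of 0.01 and, with lonelier people more often missing, -0.03. With nothing missing it was 0.02. Forcing 2% against 8%, again with lonelier people more often missing, gave 0.59 points.

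**7. Skipped items.** If each item is skipped independently at 0.1%, 0.25%, 0.5% or 1% (assumed), 1 - (1 - q)^20 gives 2%, 5%, 10% or 18% incomplete totals. In simulated 20-item data with a total SD of 8.7 to 10.9, prorating 19 items had an error of about 0.7 points, and filling only the missed item with its mean about 0.8. Replacing the total by the cohort mean has an error of one full SD.

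**The case against.** The strongest reply is that the rule may hardly ever apply. Completing the intake survey is a condition of full enrolment, and nothing in the documents says that items could be skipped. This stands: the frequency is unknown and may be near zero.

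Three stronger readings are tempting, and the documents do not support them.

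- **That one skipped item always costs the whole scale.** A reader might infer this because the total needs all 20 items. The rule, however, speaks of data missing from the survey, and individual responses are kept. Filling only the skipped item is an equally open reading, with an error that cannot exceed 3 points. The plan is silent, and that silence is the defect on this point.
- **That the arm comparison is biased.** The intake survey comes before randomization and the filled mean is common to both arms. For affected people the contrast becomes a comparison of exit scores, which has the same expectation as a comparison of change scores. The 0.59-point shift needs a forced imbalance, which should arise only by chance here.
- **That the entered value is nothing but noise.** It still carries any arm effect on the exit score, and it correlates 0.39 with true change at rho 0.7. Below rho 0.5 the rule lowers the variance of DV 5.

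It is also fair to say that the stated hypothesis concerns steps and that the loneliness mediation is a secondary analysis. Neither point makes exit minus cohort average a measure of change in an outcome listed as primary.

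**Conclusion.** The point holds as a low-priority refinement. The rule is explicit. When it applies and an exit score exists, DV 5 and the loneliness mediator do not measure within-person change.

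With 5% of scores filled and rho 0.6 to 0.8, DV 5 variance rises by 1-8%. That is a standard error 0.6% to 3.7% larger (square roots of 1.0125 and 1.075). The mediator slope shrinks by about 4-9%. At 10% filled the figures are 3-15% and 7-17%. At rho 0.9 the variance rise would be 20% and 40%; at 0.5 it is nil.

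All of these rest on assumed correlations and missingness, and on equal SDs at intake and exit. The slope figures also assume that intake is related to step change only through loneliness change. No systematic arm bias in DV 5 is expected from this rule.

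**What to change.** Add two rules to the Missing data section of both documents.

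1. Score the UCLA scale at intake and at exit as 20 times the mean of the person's answered items when most are answered, with the threshold fixed in advance. Sixteen of 20 is one workable choice; the exact number is a matter of judgement.
2. If the intake total is still missing, multiply impute it using exit score, arm and the model covariates, adding step change for the mediation analysis. Do not use the cohort mean in DV 5 or in the mediator. Keep mean or mode filling for covariates such as age and gender.

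Do not set DV 5 to missing and drop these people. Below a correlation of about 0.76 that loses more precision than the present rule, and it conflicts with an ITT set meant to keep everyone who meets the inclusion criteria despite missing data.

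The cost is a few sentences and a little more analysis work, including a stated order for combining imputation with the bootstrap. The retained item responses make the scoring rule feasible with no new data.
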